### 11.9 Heterogeneity

Heterogeneity across sites will be assessed as follows. Based on completers, a (frequentist) Cox proportional hazards regression will be conducted, with a term for site included in the model. If there is not a significant site effect ( $p > 0.10$ ), data will be considered poolable across sites. If there is a significant site effect ( $p < 0.10$ ), an investigation will be conducted into whether subject baseline characteristics explain this difference. Candidate baseline characteristics include those that (1) significantly predict AFS, (2) significantly differ across sites, or (3) are deemed to be clinically important. If a baseline characteristic (or set of characteristics) explains the difference (in that inclusion of the characteristic(s) in the proportional hazards regression model causes the site effect to become non-significant,  $p > 0.10$ ), a summary Bayesian analysis of AFS adjusting for the characteristic(s) will be conducted. If baseline characteristics do not explain the difference, results will be presented by site and in various groupings of sites as appropriate (e.g., perhaps removing any markedly different sites).

The summary Bayesian analysis will be a Bayesian piecewise exponential survival regression that adjusts for the baseline characteristic(s) described above. Summaries of the posterior distribution of the 180-day AFS rate (e.g., posterior mean/median, 95% credible interval, the posterior probability that  $\phi > 0.54$ ) will be presented.

In these analyses, small sites (contributing  $< 5$  subjects) will be combined into one or more larger pseudo-sites of size  $\geq 5$  but  $\leq 10$ . An analysis omitting small sites will also be presented. Descriptive statistics will

be presented for all sites regardless of size.

- Heterogeneity analyses across the following factors (in addition to sites) will be conducted similarly:
- US/OUS
- Sex (Male/Female)
- Dialysis status (Yes/No)
- Age ( $\leq 70$ ,  $> 70$ )
- Diabetes (Type I, Type II, None)
- Race/Ethnicity

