A prospective, single-arm, multi-center pivotal study designed to confirm the safety and effectiveness of The LimFlow System. The study will consist of a minimum of 60 and up to 105 subjects. This study utilizes a Bayesian Goldilocks adaptive design for sample size determination.

Number of Sites

Up to 25 sites in the United States, United Kingdom, and Japan

Primary Endpoint

Amputation Free Survival (AFS) defined as freedom from major amputation or death at 6 months, compared to a literature-based performance goal.

Major Amputation: above-ankle amputation of the index limb or

Death: all-cause mortality

Secondary Endpoints

Primary Patency: Defined as the absence of occlusion of the endovascular intervention maintained with no additional or secondary surgical or endovascular procedures, at 30 days and 6 months.

Primary Assisted Patency: Defined as the absence of occlusion of the endovascular intervention maintained with the use of additional or secondary surgical or endovascular procedures, as long as occlusion of the primary treated site has not occurred, at 30 days and 6 months.

Secondary Patency: Defined as the absence of occlusion of the endovascular intervention that is maintained with the use of additional or secondary surgical or endovascular procedures after occlusion occurs, at 30 days and 6 months.

Limb Salvage: Defined as the percentage of subjects with freedom from above-ankle amputation of the index limb, evaluated at 30 days, 3 and 6 months.

Change in Rutherford Classification: Defined as a change of one

STATISTICAL ANALYSIS PLAN

class or greater, as evaluated at 30 days, 3 and 6 months.

Technical Success: Defined as the successful creation of an arteriovenous fistula in the desired limb location with immediate morphological success.

Procedural Success: Defined as the combination of technical success, and absence of all-cause death, above-ankle amputation or clinically driven major re-intervention¹ of the stent-graft at 30 days.

Target Wound Healing: Defined as complete healing of the patient's target wound as evaluated at 30 days, 3, 6, 9 months, and 1 year.

All Wound Healing: Defined as complete healing of the patient's wounds as evaluated at 30 days, 3, 6, 9 months, and 1 year.

All Wound Area Reduction: Defined as reduction in area of the patient's wounds as evaluated at 30 days, 3, 6, 9 months, and 1 year.

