9.5 Heterogeneity

Heterogeneity across sites will be assessed as follows. Based on completers, a (frequentist) Cox proportional hazards regression will be conducted, with a term for site included in the model. If there is not a significant site effect ($p > 0.10$), data will be considered poolable across sites. If there is a significant site effect ($p < 0.10$), an investigation will be conducted into whether subject baseline characteristics explain this difference. Candidate baseline characteristics include those that (1) significantly predict AFS, (2) significantly differ across sites, or (3) are deemed to be clinically important. If a baseline characteristic (or set of characteristics) explains the difference (in that inclusion of the characteristic(s) in the proportional hazards regression model causes the site effect to become non-significant, $p > 0.10$), a summary Bayesian analysis of AFS adjusting for the characteristic(s) will be conducted. If baseline characteristics do not explain the difference, results will be

STATISTICAL ANALYSIS PLAN

presented by site and in various groupings of sites as appropriate (e.g., perhaps removing any markedly different sites).

The summary Bayesian analysis will be a Bayesian piecewise exponential survival regression that adjusts for the baseline characteristic(s) described above. Summaries of the posterior distribution of the 180-day AFS rate (e.g., posterior mean/median, 95% credible interval, posterior probability that $\phi > 0.54$) will be presented.

In these analyses, small sites (contributing < 5 subjects) will be combined into one or more larger pseudo-sites of size ≥ 5 but ≤ 10 . An analysis omitting small sites will also be presented. Descriptive statistics will be presented for all sites.

Heterogeneity analyses across the following factors (in addition to sites) will be conducted in a similar manner:

- US/OUS
- Sex (Male/Female)
- Dialysis status (Yes/No)
- Age (≤ 70 , > 70)
- Diabetes (Type I, Type II, None)
- Race/Ethnicity

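### After an unexplained site effect, the plan allows sites to be left out because of their results; this distorts the supplementary AFS, and a model that keeps every site should replace it

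*SAP*

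**What the plan says.** SAP 9.5 starts with a test: "Based on completers, a (frequentist) Cox proportional hazards regression will be conducted, with a term for site included in the model". Sites with fewer than 5 subjects "will be combined into one or more larger pseudo-sites" of 5 to 10 subjects. Three outcomes follow.

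- p>0.10: "data will be considered poolable across sites".
- p<0.10: "If there is a significant site effect ($p < 0.10$), an investigation will be conducted into whether subject baseline characteristics explain this difference". If they do, a covariate-adjusted Bayesian piecewise exponential analysis is added. It reports the 180-day AFS and the posterior probability that it exceeds 0.54.
- p<0.10 and not explained: results are "presented by site and in various groupings of sites as appropriate (e.g., perhaps removing any markedly different sites".

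The SAP then extends the procedure to US/OUS, sex, dialysis, age, diabetes and race/ethnicity: "Heterogeneity analyses across the following factors (in addition to sites) will be conducted in a similar manner". Protocol 11.9 has the same text with a small change of wording: "Heterogeneity analyses across the following factors (in addition to sites) will be conducted similarly".

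The primary decision is fixed elsewhere. SAP 4 allows one primary hypothesis test, SAP 5.1 makes mITT the primary population, and SAP 6.2 and 6.4 compare the final posterior probability with 0.977. Section 9.5 sits under Other Analyses.

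**The concern.** A site can stand out as different only through its amputations and deaths, so leaving it out is selection on the endpoint. The plan does not say how different a site must be, on what scale, in which direction, or how many may go. With at most 105 subjects and "Up to 25 sites in the United States, United Kingdom, and Japan", most sites will be small, and extreme site rates will be common by chance alone. Whoever forms the groupings will already have seen the results.

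At stake is how a borderline primary result is read. A grouping without the poorest site will usually look better than the trial did. A reader who sees it next to a pooled result just short of the goal could take it as evidence that the device works once an outlying site is set aside.

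**Working it through.** **1. The plan's own figures.** The documents give no error rate for the heterogeneity procedure. The nearest stated figures are the exact binomial sample sizes in SAP 6.3. They reproduce: N=101 gives power 0.909 at AFS 0.70 and 0.814 at 0.68, and N=56 gives 0.915 at 0.75. With 10% missing, 101/0.9 = 112.2, so 113, and 56/0.9 = 62.2, so 63.

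**2. Inputs.** From the SAP: N=105 (maximum, section 4), goal 0.54 and threshold 0.977 with a Beta(1,1) prior (6.2), site flag at p<0.10 and small-site pooling (9.5). Assumed: 11 or 15 sites of near-equal size after pooling, the same true AFS of 0.54 at every site, complete data, and one site dropped.

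**3. Formulas.** Site k has n_k subjects and x_k event-free at day 180; p is the pooled rate; K is the number of sites.

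- Site flag, a chi-square stand-in for the Cox site test: X² = Σ (x_k − n_k·p)² / [n_k·p·(1−p)] on K−1 degrees of freedom, p-value below 0.10.
- Yardstick: with s event-free of n, Pr(φ>0.54) under Beta(1+s, 1+n−s) exceeds 0.977.

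**4. How little it takes.** With n=105 the yardstick needs s≥67 (63.8%). With n=98, one site of 7 removed, it needs s≥63 (64.3%). A trial with 65/105 (61.9%) misses. Remove a site with 2/7 and it becomes 63/98 (64.3%), which passes. This shows the arithmetic only; it does not say that the site test would fire in that trial.

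**5. Simulation with no site differences.** 200,000 trials for each number of sites; rows below the first are among flagged trials.

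| | 11 sites | 15 sites |
|---|---|---|
| Site flag | 9.6% | 9.4% |
| All sites: exceeds 0.977 | 2.6% | 2.6% |
| Drop worst: shift in AFS | +3.6 points | +3.0 points |
| Drop worst: exceeds 0.977 | 8.3% | 8.3% |
| Drop best: shift in AFS | −3.4 points | −2.8 points |
| Drop best: exceeds 0.977 | 0.3% | 0.6% |
| Drop most deviant, either direction: shift | +0.5 points | +0.5 points |
| Drop most deviant: exceeds 0.977 | 6.4% | 6.7% |

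Further runs of the same kind with 11 and 15 sites gave 7.7 to 8.9% after dropping the worst site, 6.6 to 6.9% after dropping the most deviant, and 2.7 to 2.8% with all sites. Fair summary values are 8 to 9%, about 7%, and 2.6 to 2.8%.

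**6. A different layout.** With 20 sites of unequal size before pooling, the SAP 6.7 hazards and a Cox score test, the worst-site results at AFS 0.54 among flagged trials were:

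- N=105: +2.9 points; 7.6% exceed 0.977, against 1.9% with all sites.
- N=60: +4.8 points; 10.0% against 2.1%.

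The site test itself fired in 17% (N=105) and 16% (N=60) of trials, above its nominal 10%, because sites are sparse.

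**7. Unconditional size.** Even if the reduced result could replace the primary, the 11-site case would add 0.096 × (0.083 − 0.026) = 0.0055, about half a percentage point. In the 20-site layout at N=105 the false-positive rate would go from 2.6% to 3.6%. The documents do not allow that replacement.

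**The case against.** The strongest reply is that the primary result is already protected. There is one test, in one population, against one threshold, and no exception refers to 9.5. That stands in full. A reader might infer that the trial's type I error is inflated; the documents do not support this.

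The plan also attaches no posterior probability or success threshold to the site groupings. Only the covariate-adjusted analysis, which removes no site, reports the probability of exceeding 0.54. The 0.977 yardstick above is therefore a way to measure the distortion and not a test that the plan makes. By-site results would also be shown, so an omitted site would stay visible.

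Removal is an optional example, reached only after a site flag and a failed search for explanatory characteristics. The simulation leaves out that search and assumes the option is used. No direction is prescribed, and dropping the best site lowers AFS. These points limit how often the problem arises. They do not make outcome-based removal a sound method: even an even-handed rule that drops the most deviant site more than doubles the yardstick rate.

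A second tempting reading is that seven tests at 0.10 need family control. If nothing differs, the chance of at least one flag is 1 − 0.9^7 = 0.52 for independent tests and 0.40 at a correlation of 0.5. But the pooling sentence is worded for sites only, and no adverse pooling verdict is defined for the other six factors. A flag opens an investigation, and the any-factor rate is not the rate at which site removal comes into play. A lenient screen is meant to avoid missing real differences. Testing each factor at 0.10/7 = 0.0143 would cut power for a hazard ratio of 2 with 32 events (assumed) from 62% to 31% with a 50:50 split, and from 47% to 19% with a 20:80 split. The 40 to 52% is worth knowing when a flag is read; it is not an error to correct.

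**Conclusion.** The concern holds for the site-removal clause alone. Among flagged trials with no real site differences, at N=105 and true AFS 0.54, dropping the worst site adds about 3 to 3.6 points to AFS. It takes the share exceeding 0.977 from 2.6–2.8% to about 8–9%, or to about 7% if the most deviant site is dropped. In the either-direction case the mean shift is small, and the problem is mainly that selection widens the spread of possible results.

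These figures rest on assumed site numbers and sizes, complete data, a chi-square stand-in for the Cox test, and one site removed. A less even site layout gives a similar picture (7.6% against 1.9%), and a smaller trial a somewhat larger effect. The damage is to a supplementary estimate and how it is read beside a borderline primary. This is a cheap improvement to the plan and does not touch the validity of the primary test.

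**What to change.** In SAP 9.5 and Protocol 11.9, delete the example that allows differing sites to be removed, and the open-ended site groupings that it illustrates. In their place, for a site effect that baseline characteristics do not explain, specify:

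1. The already planned Bayesian piecewise exponential regression with a random site effect, keeping every site. State the prior for the between-site standard deviation in advance. Report the between-site variation and the 180-day AFS with its 95% credible interval.
2. A leave-one-site-out display for every site or pseudo-site, in one table or plot, so that high and low sites are treated alike and none is chosen after the fact.

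Keep the by-site results and the planned analysis omitting small sites, which selects on size and not on outcome. Leave the 0.10 screen for the other six factors as it is.

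The cost is a wording change in two documents, one extra model and one display. With small sites the data say little about between-site variance, so that part of the model will lean on its prior, and the report should say so.

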9.6 Exploratory Multivariate Analysis

Potential contributing factors for AFS failures will be investigated as follows:

Using frequentist Cox proportional hazards regression models, the following variables will be investigated in univariate models:

- Sex (Male/Female)
- Dialysis status (Yes/No)
- Age (≤ 70 , > 70)
- Diabetes (Type I, Type II, None)
- Race/Ethnicity
- Rutherford Classification
- Wound Area (continuous measure)

Any variable that is significantly related to AFS (at the 0.10 level) will be entered into a Cox multiple regression model. Variables no longer significant at the 0.05 level will be removed via backward elimination. The final model will be presented.

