	Baseline and Screening (-6M to proc)	Treatment (Day 0) to Discharge	2 Weeks (+/- 3 Days)	1 Month (+/- 1 week)	2 Month (+/- 2 weeks)	3 Month (+/- 2 weeks)	6 Month (+/- 2 weeks)	9 Month (+/- 2 weeks)	1 Year (+/- 4 weeks)	2 Year (+/- 4 weeks)	3 Year (+/- 4 weeks)
Written Informed Consent	√										
Baseline imaging  that establishes pedal artery target	√										
Inclusion / Exclusion criteria, including IRC, assessment that subject is not a candidate for conventional surgical or endovascular limb salvage procedures	√										
Demographic data, medical history, medication review, physical exam, and pregnancy test (if applicable)	√										
Additional exams if required to confirm eligibility 	√										
Pedal vein assessment for case planning	√										
Review of medications / dual anti-platelet regimen 	√	√	√	√		√	√	√	√	√	√
Rutherford Classification (RCC)	√			√		√	√	√	√	√	√
WIFI Classification (ischemia measured via TcPO 2  or Toe Pressure)	√		√	√		√	√	√	√	√	√
Wound healing assessment, and photographs 	√		√	√		√	√	√	√	√	√
Wound culture, if suspected infection 	√	√	√	√		√	√	√	√	√	√
Pulse evaluation via hand-held continuous wave Doppler distal to the stent graft 		√ 	√	√		√	√	√	√	√	√
Serum Creatinine	√			√			√				
Numeric Pain Scale Rating (1-10)	√			√		√	√	√	√	√	√
Procedural angiogram  and device performance data		√									
Procedure time, defined from sheath insertion to final catheter removal		√									
Fluoroscopy and Contrast for the index procedure		√									
Device- or procedure-related AE and SAEs 		√	√	√	√	√	√	√	√	√	√
Assessment of amputation and/or re-intervention of the Stent Graft			√	√		√	√	√	√	√	√
Duplex Ultrasound Exam to assess Stent Graft patency 				√	√	√	√	√	√	√	√
All-cause mortality		√	√	√	√	√	√	√	√	√	√

 E.g., an angiogram without procedure or angiogram from a failed recanalization  
 Including an MRI, if there is suspected osteomyelitis and bypass conduit vein mapping if there is a pedal artery target and the ipsilateral saphenous vein has not been previously harvested  
 Dual antiplatelet therapy is recommended for 3 months post-procedure. At a minimum, all subjects are recommended to be started on DAPT at least one week before procedure or adequately pre-loaded with DAPT as per institution practice.  

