Freedom from Contrast-Induced Nephropathy: Defined as subjects without acute (within 72 hours after intravenous contrast administration) impairment of renal function, measured as an absolute ≥ 0.5 mg/dL (44 $\mu\text{mol/L}$) increase compared to baseline SCr value.

Procedure Time: Defined as the time of the first puncture (venous or arterial) to when the last catheter is removed.

Radiation Exposure: Defined as patient radiation exposure (in milligray) during the procedure.

Contrast Volume: Defined as the total volume of contrast media (in milliliters) given during the procedure.

Inclusion Criteria

- 1) Subject must be > 21 and < 95 years of age
- 2) Clinical diagnosis of critical limb ischemia, defined as the following clinical assessments: previous angiogram or hemodynamic evidence of severely diminished arterial inflow of the index limb (e.g., $\text{ABI} \leq 0.39$, $\text{TP} / \text{TcPO}_2 < 30$ mm Hg) and:
 - a. Rutherford Classification 5, ischemic ulceration OR

¹ The creation of a new surgical bypass, the use of thrombectomy or thrombolysis (i.e., procedures done in the setting of lost primary-assisted patency), or major surgical revision such as a jump graft or an interposition graft performed for occlusion of the stent graft.

STATISTICAL ANALYSIS PLAN

- b. Rutherford Classification 6, ischemic gangrene
- 3) Subject has been assessed by the Principal Investigator, reviewed by the Independent Review Committee (IRC), and determined that no conventional distal bypass, surgical or endovascular therapy for limb salvage is feasible due to either a) absence of a usable pedal artery target (endovascular or surgical approach), or b) the presence of a pedal artery target with absence of a viable single-segment vein in either lower extremity or either arm that could be used for autogenous vein conduit.
- 4) Proximally, the Target In-flow Artery at the cross-over point must fall within the recommended vessel diameter ranges for the LimFlow stent graft by visual estimation.
- 5) Prior stent(s) to the infrainguinal arteries (e.g., iliac, SFA, and popliteal) are allowed.
- 6) Planned minor amputation (e.g., partial toe, ray or proximal foot/transmetatarsal) of target extremity within 30 days after the index procedure is allowed.
- 7) Subject is willing and able to sign the informed consent form.

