6.3 Sample Size Considerations

Although the analysis methods are Bayesian, the following frequentist scenarios are used to guide the determination of minimum and maximum sample size.

- According to PASS 13³, when using $\alpha = 0.025$ (one-sided) in an exact binomial test, achieving 90% power to test the hypotheses in Section 6.1 when the true AFS = 0.70 would require a sample size of 101 subjects. Allowing for 10% missing data would require a sample size of N=113 subjects
- If the true AFS = 0.68, a sample size of 101 subjects would achieve 81% power. Allowing for 10% missing data would require a sample size of N=113 subjects

³ PASS 13 Power Analysis and Sample Size Software (2014). NCSS, LLC. Kaysville, Utah, USA, ncss.com/software/pass

STATISTICAL ANALYSIS PLAN

- If the true AFS = 0.75, 90% power requires a sample size of N=56 subjects. Allowing for 10% missing data would require a sample size of N=63 subjects.

There is considerable uncertainty in the true AFS rate ϕ . Consequently, it is desirable to utilize a study design that achieves at least 80% power when AFS ≥ 0.68 and 90% power when AFS ≥ 0.70 , while allowing early stopping of enrollment if the AFS rate proves to be very high (e.g., 0.75) or very low (≤ 0.54). Therefore, a study design is selected wherein the sample size is adaptively determined, with a minimum value of 60 and a maximum value of 105.

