The censoring mechanism applied to these simulated event times is induced by the accrual rates, the timing of analyses, and by a random dropout pattern. For every simulated subject, a study start time is assigned according to an assumed accrual pattern, and when an analysis occurs, such as the first sample size evaluation when 60 subjects have been enrolled, each simulated subject's event time is censored at that time (if an event has not previously occurred for that subject). In addition, a designated fraction of simulated subjects is randomly chosen to be lost to follow-up at random times that are uniformly distributed over their 180-day study period, and these subjects are censored at the minimum of the dropout time and the analysis time (assuming they have not yet had an event). For other analysis times (interim or final), censoring times are simply re-computed based on the new time of analysis, and some simulated subjects who did not have an event at the first sample size analysis may have events at a subsequent analysis.

Lost to Follow-up / Data Missingness

Simulations were conducted under the assumption of 10% lost to follow-up (LTFU) over the 6-month study period. With each simulated trial, each subject was designated to be "lost" with probability 0.10; thus, the exact number of subjects designated to be lost from one simulated trial to the next varied, though on average it was 10%. Furthermore, those subjects designated as "lost" were assumed to have been lost uniformly in time over the 6-month period. Subsequent to this, subjects were assigned event times. If the event time occurred after the LTFU time, that subject was considered censored at the LTFU time, whereas if the event time occurred before the LTFU time, that subject had an observed event at the event time.

Rate of Accrual

The speed at which subjects are recruited into the trial is an important assumption embedded within the simulations to determine operating characteristics. The expected rate of accrual into the analysis population is 5 subjects/month, after an initial ramp-up period for the first 7 months of 1, 2, 2, 3, 3, 4, and 4 subjects/month. This "expected" accrual rate was used in the generation of operating characteristics shown in Table 2.

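### SAP 9.6 splits age at 70 in the exploratory Cox models without giving a reason; entering age as a continuous variable would keep more of its information at almost no cost

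*SAP*

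**What the plan says.** SAP 9.6 lists seven candidate factors for univariate Cox models of AFS failure. Age is one of them, as a two-level factor divided at 70. The last item is "Wound Area (continuous measure"), so the plan already accepts an unsplit covariate in this model. Nothing in 9.6 explains the cut.

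Two significance filters follow. Entry: "Any variable that is significantly related to AFS (at the 0.10 level) will be entered into a Cox multiple regression model". Retention: "Variables no longer significant at the 0.05 level will be removed via backward elimination". The section does not say whether these levels are one-sided or two-sided; I take them as two-sided.

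The same split is used in the subgroup summaries (SAP 9.2, Protocol 11.6) and the heterogeneity analyses (SAP 9.5, Protocol 11.9).

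Neither document names a field for age in years, but eligibility depends on it: "Subject must be > 21 and < 95 years of age" in the SAP synopsis. Protocol inclusion criterion 1 sets different limits, which are also numeric. The baseline column of Protocol Table 1 includes "Demographic data, medical history, medication review, physical exam, and pregnancy test (if applicable"). That age in years is available is therefore a safe inference, though not a documented statement.

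**The concern.** Splitting a continuous covariate treats everyone on one side of the cut as alike. If risk changes gradually with age, the coded variable carries less information than age itself, and its test has less power. Here the loss matters more than in a descriptive table, because the univariate test decides whether age reaches the multiple model at all. A real age effect is more likely to be screened out when coded at 70 than when coded in years.

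What is at stake is the quality of an exploratory description of which factors go with amputation or death. The performance-goal test does not use this model.

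**Working it through.** **Inputs from the documents**

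- Maximum sample size 105: "the sample size is adaptively determined, with a minimum value of 60 and a maximum value of 105" (SAP 6.3).
- Design AFS rate 0.70: 90% power "when the true AFS = 0.70 would require a sample size of 101 subjects" (SAP 6.3).
- Dropout: "Simulations were conducted under the assumption of 10% lost to follow-up (LTFU) over the 6-month study period" (SAP 6.7).
- Entry level 0.10 and retention level 0.05 (SAP 9.6).

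**Inputs that are assumptions**, because the documents do not give them: the hazard ratio per SD of age, the age distribution, the share of subjects above 70, and the shape of the age effect. I take a log-linear effect, roughly normal age and 70 at the median, and vary the hazard ratio.

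**The plan's own figures.** The SAP states no power, effect size or event count for 9.6, so there is no figure for this model to reproduce. The sample-size figures that supply the AFS rate do reproduce. For the exact binomial test of 0.54 at one-sided 0.025, the smallest n with 90% power at AFS 0.70 is 101 (reject at 65 or more; alpha 0.0227; power 90.9%). Power at 0.68 with that n is 81.4%.

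**Events.** 105 × (1 − 0.70) = 31.5, about 32 before dropout.

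**Information kept by the split.** For a normal covariate cut at c, with a share q on one side, the fraction kept is φ(c)² / [q(1 − q)]. At the median this is (1/2π)/0.25 = 2/π = 0.637, so about 36% is lost. This fraction does not depend on the hazard ratio, but it does depend on normality, linearity and the position of the cut.

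**Power at the 0.10 screen.** For continuous age, z = ln(HR) × √32. For the split, z is multiplied by √(2/π) = 0.798. Power = Φ(z − 1.645).

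| HR per SD | z continuous | z split | Power continuous | Power split |
|---|---|---|---|---|
| 1.3 | 1.48 | 1.18 | 44% | 32% |
| 1.5 | 2.29 | 1.83 | 74% | 57% |
| 1.7 | 3.00 | 2.39 | 91% | 77% |

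With 31.5 events unrounded, the middle row is 73.6% and 56.8%.

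**Sensitivity to the inputs**

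- *Dropout.* Simulated Cox score tests with 10% uniform loss (8,000 trials, about 30 events) give 71% and 52% at HR 1.5.
- *Number of events, HR 1.5.* 18 events: 53% and 39%. 48 events (AFS 0.54): 88% and 73%. At the average N of 82.5 in SAP Table 2 for AFS 0.70, events are 82.5 × 0.30 = 24.75 and power is about 65% and 49%.
- *Effect size, 31.5 events.* HR 1.2: 27% and 20%. HR 2.0: 99% and 93%. The gap is small when power is very low or very high.
- *Position of the cut, HR 1.5, 31.5 events.* With 30% or 20% of subjects on one side of 70, the formula gives split power of 53% or 48%. The formula treats the two sides alike, but simulation does not. With 70% of subjects above the cut and 10% loss, split power was about 43%. An off-centre cut need not cost more when the smaller group is the older one.
- *Retention level 0.05, HR 1.5, 31.5 events, taken as a single test.* 62% and 44%.
- *Shape.* If risk steps up at the cut itself (HR 2.0 between the groups, simulated), the split does better: 58% against 44%.

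**The case against.** The strongest reply is that this is a modelling preference in an analysis labelled exploratory. The cut is pre-specified and is the same in 9.2, 9.5 and 9.6. That keeps the displays consistent and rules out a cut chosen from the data. If risk really changes at about 70, the split is the better coding. Continuous coding would not secure adjustment for age either: in the illustration, age in years still fails the 0.10 screen about 26% of the time (100 − 74) and then faces the 0.05 retention rule.

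Much of this stands. The plan contains no contradiction here, and the gain is limited. A step at 70 is possible, but the documents do not suggest one. A continuous term also needs no cut, so it is no more open to choice after the fact. Consistency with 9.2 is kept if the split stays there for display.

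Three stronger readings are tempting, and the documents do not support them.

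- *That the split lowers power from 74% to 57% as a fact of this plan.* The hazard ratio, age distribution and effect shape are all assumed. Other combinations, such as 23.6 events with HR 1.6, give the same pair.
- *That 9.6 is the only analysis of which patients fail.* SAP 9.2 summarises AFS by age and other factors, and 9.5 looks at age and at characteristics that predict AFS. Only the multivariable selection is particular to 9.6.
- *That losing age distorts the coefficients for dialysis, diabetes or Rutherford class.* This would require age to be associated with those factors in this cohort. The documents report no such association, and no size of bias can be derived from them.

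**Conclusion.** The point holds as a small improvement to an exploratory analysis. The coding is documented, unexplained, and out of line with the treatment of wound area in the same list. The loss of about 36% of the information on age rests on a log-linear effect and on 70 lying near the median of a roughly normal distribution.

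At about 32 events, the loss in power at the entry screen is 12 to 17 percentage points for hazard ratios of 1.3 to 1.7 per SD. It is about 19 points at 1.5 once the SAP's dropout is included. It is smaller for very weak or very strong effects, and it reverses if risk steps at the cut. The primary endpoint test, its threshold and its type I error are not affected.

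**What to change.** In SAP 9.6, replace the two-level age factor with age as a continuous variable, reported per 10 years, in both the univariate and the multiple Cox models. The 10-year scaling only makes the hazard ratio easier to read; it does not change the test. Keep the 70-year split for the descriptive subgroup display in SAP 9.2.

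The cost is one line of SAP text. No new data should be needed, since the eligibility limits already require age in years to be known. The sample size, interim rules and primary analysis stay as they are. The change should be recorded before the exploratory models are run.
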